- H:** Blood samples will be collected to assess IR and analyzed in the central laboratory. Subjects should have a 4-day washout after last FVIII injection before blood draws if possible. A pre-dose blood sample will be drawn. Subjects will then receive their prophylaxis dose of rVIII-SingleChain injection in the clinic. For on-demand subjects, the usual dose used to treat a bleeding episode or any other dose determined by the investigator will be administered in the clinic. A post-dose blood sample will be drawn 30 to 60 minutes (\pm 5 minutes) after injection. Incremental recovery will be collected at Day 1, at the closest visits after 10 EDs, after 50 EDs, and after 100 EDs (see [Section 8.6.2](#)).
- I:** Blood samples for inhibitors to FVIII, antibodies against rVIII-SingleChain, and antibodies to CHO proteins will be collected at Screening and at the closest visit after 10 EDs, after 50 EDs, and after 100 EDs. For the inhibitor blood samples, subjects should have a 4-day washout from last FVIII injection before blood draw if possible.
- J:** If the investigator collects blood samples for FVIII levels or inhibitor assessment at any other time during the study, the local laboratory results must be recorded in the eCRF and a duplicate sample must be submitted for analysis to the central laboratory (see [Section 8.6](#)).
- K:** Virology retention samples: The Visit 1 sample must be taken before first rVIII-SingleChain injection. CSL will retain samples for 5 years from EOS.
- L:** rVIII-SingleChain may be dispensed at more frequent schedules if need is determined by the investigator.
- M:** Unused vials near expiration or with insufficient shelf life to cover time duration until next visit should be returned at the next scheduled visit. All unused vials will be returned at the EOS visit.
- N:** The observation period for adverse event (and serious adverse event) reporting in an individual subject will start at the time of giving written informed consent for participation in the current study and finish with the EOS visit. However, adverse events ongoing at the EOS visit will be followed until resolution or 28 days after the final administration of rVIII-SingleChain during this study, whichever is sooner.

Schedule of Assessments for Surgery Substudy (Arms 1, 2 and 3)

Period	Before surgery	During Surgery	After Surgery
Body weight	X		
Hemoglobin measurement	X		X ^A
Predicted intraoperative estimated blood loss during surgery	X		

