2.2.2.2 Safety

In **Arm 1 and Arm 3 (PTPs)**, the secondary safety endpoints are:

- Incidence of inhibitor formation to FVIII in at least 200 PTPs after 10 EDs and after 50 EDs with rVIII-SingleChain.
- Percentage of PTPs who develop antibodies against rVIII-SingleChain.
- Percentage of PTPs who develop antibodies to CHO proteins.

In **Arm 2 (PUPs)**, the secondary safety endpoints are:

- Incidence of high-titer inhibitor formation to FVIII (ie, inhibitor titer of ≥ 5 BU/mL) after 10 EDs with rVIII-SingleChain in PUPs.
- Incidence of low-titer inhibitor formation (ie, inhibitor titer of < 5 BU/mL) to FVIII after 10 EDs and after 50 EDs with rVIII-SingleChain in PUPs.
- Incidence of total (low- and high-titer) inhibitor formation to FVIII after 10 EDs and after 50 EDs with rVIII-SingleChain in PUPs.
- Percentage of PUPs who develop antibodies against rVIII-SingleChain.

- Percentage of PUPs who develop antibodies to CHO proteins.
- Percentage of PUPs with clinically significant abnormal values for blood pressure, or heart rate, or body temperature at 1, 2, 3, or 6 hours after the first rVIII-SingleChain injection.
- Percentage of PUPs with treatment-emergent clinically significant abnormal values for blood pressure, heart rate, or body temperature during the course of the study.

2.3

CCI [Redacted]

2.3.1

CCI [Redacted]

2.3.2

CCI [Redacted]

CCI [Redacted]

CCI

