8.6.1 Blood Samples for Inhibitors and Antibodies

The presence of inhibitors to FVIII, antibodies against rVIII-SingleChain, and antibodies against CHO proteins will be analyzed by the central laboratory. For the inhibitor blood samples, subjects should have a 4-day washout from last FVIII infusion before blood draw if possible.

1. In **Arms 1 and 3 (PTPs)**, blood samples for inhibitors to FVIII, antibodies to rVIII-SingleChain, and antibodies to CHO proteins will be collected at the closest visits after 10 EDs, after 50 EDs, and after 100 EDs as outlined in [Table 8](#).
2. In **Arm 2 (PUPs)**, blood samples for inhibitors to FVIII, antibodies against rVIII-SingleChain, and antibodies to CHO proteins will be collected at all scheduled visits.

Blood samples drawn for inhibitor assessment should be sent to the central laboratory for testing with the Nijmegen assay. A subject will be considered to have developed an inhibitor if the titer result is ≥ 0.6 BU/mL and verified by repeat testing. FVIII inhibitors will be further categorized as low-titer (≤ 5 BU/mL) and high-titer (> 5 BU/mL). If an inhibitor is suspected, all inhibitor testing must be expedited and a repeat sample obtained as soon as possible to confirm results.

Details regarding sample collection, handling, deep freezing of samples and shipment to the central laboratory are given in the Laboratory Manual in the Investigator Site File.

If an inhibitor is suspected (eg, lack of efficacy of IMP), additional visits may be scheduled for inhibitor assessment. If a subject undergoes surgery, blood samples will be collected at least 28 days after surgery to test for inhibitors to FVIII, antibodies against rVIII-SingleChain, and antibodies against CHO proteins in all study arms. In addition, a pre-surgery blood sample for inhibitor testing is recommended for PUPs in Arm 2.

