11.3.3.2 Primary Safety Analysis

The incidence of inhibitor formation to FVIII, based on the number of EDs and subjects specified in [Section 11.3.3.1](#) will be reported together with a (2-sided) 95% CI. However, if no inhibitor formation is observed, then the upper one-sided 97.5% confidence limit will be reported. For calculation of the incidence for each study arm, the numerator will include all subjects who develop inhibitors in each arm and the denominator will include:

- a) all PTPs with at least 100 EDs plus PTPs with less than 100 EDs but with inhibitors.
- b) all PUPs with at least 50 EDs plus PUPs with less than 50 EDs but with high-titer inhibitors.

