#### 4.7.1 Incidence of Inhibitor Formation

The incidence of inhibitor formation to FVIII will be estimated for subjects in the Safety population who did not have inhibitors at baseline. Baseline assessments are defined as those assessments done before date and time or on the same date and time of the first dose. If time of inhibitors assessment or time of first dose is missing then the inhibitor result taken at the same date of the first dose will be considered as baseline. Inhibitor formation will be defined as any post-baseline inhibitor titer  $\geq 0.6$  BU/mL identified and confirmed by re-testing at a subsequent visit. Both tests must be performed by a central laboratory. A positive result not confirmed as positive by re-testing at a subsequent visit result will be considered as non positive. In the KM analysis of inhibitor occurrence, the first positive result will be considered as an event. A positive result not confirmed as positive by re-testing at a subsequent visit result will not be considered as an event. Positive FVIII inhibitors will be further categorized as low or high titer. Low-titer inhibitors are defined as positive inhibitors with a titer of  $\leq 5$  BU/mL. High-titer inhibitors are defined as positive inhibitors with a titer of  $> 5$  BU/mL.

For the inhibitor incidence after 10 Total EDs, the numerator will include all subjects with inhibitors observed at the closest visit up to 10 EDs ( $\leq 10$  EDs). The denominator will include all subjects with at least 10 EDs ( $\geq 10$  EDs) plus subjects with less than 10 EDs but with inhibitors.

- Numerators = Number of PTP subjects who develop inhibitors up to 10 EDs ( $\leq 10$  EDs)
- Denominators = Total number of PTPs with at least 10 EDs ( $\geq 10$  EDs) + subjects with less than 10 EDs with inhibitors. Subjects not tested at  $\leq 10$  EDs will be excluded.

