##### The Inhibitor incidence after 100 Total EDs

- Numerators = Number of PTP subjects who develop inhibitors up to 100 EDs ( $\leq 100$  EDs)
- Denominators = Total number of PTPs with at least 100 EDs ( $\geq 100$  EDs) + subjects with less than 100 EDs with inhibitors. Subjects not tested at  $\leq 100$  EDs will be excluded.

CCI

Same algorithm will be applied for PUPs.

For PUPs incidence of transient inhibitors (negative results within 6 months after positive result) will be also provided.

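### SAP 4.7.1 counts PTP inhibitors only up to 10, 50 and 100 EDs, but samples are drawn after those milestones, so a case first found at the after-100-ED sample enters none of the three rates

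*SAP*

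**What the plan says.** **Endpoints.** The PTP primary endpoint (Protocol 2.1.2, SAP 2.1) is inhibitor incidence in at least 200 PTPs with at least 100 EDs. The secondary endpoint (Protocol 2.2.2.2) is "Incidence of inhibitor formation to FVIII in at least 200 PTPs after 10 EDs and after 50 EDs with rVIII-SingleChain".

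**Sampling.** Under Protocol 8.6.1, PTP samples "will be collected at the closest visits after 10 EDs, after 50 EDs, and after 100 EDs". Note I to the Arm 3 schedule says the same: they "will be collected at Screening and at the closest visit after 10 EDs, after 50 EDs, and after 100 EDs". PTP visits are every 3 months ±7 days, with a month defined as 28 days. The End of Study sample comes after at least 100 EDs (Protocol 8.10.6). In Arm 1, EDs accumulate from the lead-in study; in Arm 3 they start in this study (Protocol 8.6.2, Table 8 note A).

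**Counting.** In SAP 4.7.1, "the numerator will include all subjects with inhibitors observed at the closest visit up to 10 EDs", with ≤10 EDs stated in brackets. The 100-ED rule reads "Numerators = Number of PTP subjects who develop inhibitors up to 100 EDs" (≤100). Its denominator is PTPs with at least 100 EDs plus "subjects with less than 100 EDs with inhibitors. Subjects not tested at" or below 100 EDs are then excluded. For Arm 2 the SAP adds: "Same algorithm will be applied for PUPs". Protocol 11.3.3.4.1 has the same caps but not the exclusion.

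**Primary rule.** In Protocol 11.3.3.2, "the numerator will include all subjects who develop inhibitors in each arm", with no ED cap.

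**The concern.** The caps look backwards from each milestone; the samples look forwards. A sample taken after 10 EDs cannot count in a rate limited to ≤10 EDs unless it falls exactly on ED 10. At 10 and 50 EDs the result is a one-milestone delay. At 100 EDs there is no later rate to catch the case, so it drops out of the numerator, while a subject tested earlier stays in the denominator as a non-event.

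This bears on the PTP primary endpoint. The visible SAP text has one 100-ED formula and it is capped, while the protocol's primary analysis is uncapped. The two documents can give different answers, and the SAP version can report zero when an inhibitor was found at the very sample meant to detect it.

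The exclusion of subjects not tested at ≤X EDs adds a second problem. It is not in Protocol 11.3.3.4.1, and the visible text of SAP 4.11 does not list it as a change. With no scheduled post-dose sample at ≤10 EDs in Arm 3, that arm contributes 0/0 to the 10-ED rate, or 0/N if the screening sample counts as a test.

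**Working it through.** The plan states no rate or power to reproduce; the sample size follows a guideline (Protocol 11.1). The check maps each sample to the caps.

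**Inputs.** Visit interval 3 × 28 = 84 days, ±7 days. Dosing of 2 per week, 3 per week or every second day is an assumption, taken from the usual regimens in earlier studies (Protocol 3.2.1). That gives 24, 36 or 42 EDs per interval.

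**PTP starting at ED 0 (fits Arm 3), ED at the first visit at or after each milestone:**

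| Dosing | After 10 | After 50 | After 100 |
|---|---|---|---|
| 2/week | 22–26 | 50, or 70–74 | 118–122 |
| 3/week | 33–39 | 69–75 | 105–111 |
| Every second day | 39–46 | 81–88 | 123–130 |

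No after-10 or after-100 sample meets its cap. The one exact hit is at 50 EDs on 2/week, when the preceding visit falls on one of 4 of its 15 allowed days (4/15 = 27%).

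**Other constant rates.** A start at ED 0 with k EDs per interval hits a milestone exactly at nominal visits only if k divides it. Of the 19 values k = 24 to 42, none divides 10, and only k = 25 divides 50 or 100.

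**Arm 1, any start from ED 0 to 99.** Stepping by 24, 36 or 42, the first visit at or after 100 EDs lands exactly on 100 for 4, 2 and 2 of 100 starts. It lies above the cap for the other 96, 98 and 98. The mean ED at that visit is 111.9, 118.6 and 122.6.

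**Effect on the rate.** Take 200 PTPs (the target minimum) with one inhibitor first found at the after-100 sample, and exact (Clopper-Pearson) limits as in SAP 4.7.1:

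- Uncapped: 1/200 = 0.5%. Lower limit 1 − 0.975^(1/200) = 0.01%; upper limit 2.75% (97.5% quantile of Beta(2, 199)).
- Capped: 0/200. One-sided 97.5% upper limit 1 − 0.025^(1/200) = 1.83%.

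**PUPs on prophylaxis.** Visits are every 28 days until 25 EDs, then every 84 days (Protocol 8.10.2.1.3). Nominal visits fall at:

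- 2/week: ED 8, 16, 24, 32, 56
- 3/week: ED 12, 24, 36, 72
- Every second day: ED 14, 28, 70

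The last test at or before ED 50 is at ED 32, 36 or 28, and the next at ED 56, 72 or 70. An inhibitor arising in between, before ED 50, is missed by the ≤50 cap. On-demand PUPs are tested 1 month after each dose, so this gap does not apply to them.

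For size, Protocol 1.1 cites 35.4% for all inhibitors: 0.354 × 24 = 8.5. With 8/24 the rate is 33.3% (15.6% to 55.3%). Omitting one gives 7/24 = 29.2% (12.6% to 51.1%), a change of 1/24 = 4.2 points. This illustrates the total-inhibitor rate, not the high-titer primary.

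**The case against.** **The primary analysis is not shown to be capped.** Protocol 11.3.3.2 governs it; the caps come from a protocol section on intermediate timepoints. SAP 4.7.1 opens with an uncapped definition of inhibitor formation, SAP 2.1 words the PUP primary endpoint as during the study, and SAP 4.11 announces no change to the primary numerator. Redacted blocks follow the 100-ED formula. This stands as a reason to call the SAP ambiguous rather than a deliberate replacement. But the opening text defines an event, not a rate, and the visible SAP never states the uncapped primary rate.

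**The case would appear elsewhere.** This is true. Confirmed inhibitors are SAEs (Protocol 9.1.3). SAP 4.7.1 also summarizes incidence at the 10-, 50- and 100-ED assessments recorded in the eCRF, and a time-to-inhibitor analysis is planned. None of these corrects the written numerator, and the eCRF summary uses current-study EDs with no stated numerator or denominator.

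**The figures assume regular dosing and, at 10 and 50 EDs, a start at ED 0.** This also stands in part. Arm 1 subjects may have lead-in samples inside a cap, and unscheduled, post-surgery or early-withdrawal samples may fall there too. Infrequent on-demand dosing brings the sample closer to the milestone. Arms 1 and 3 are reported together, so the 0/0 is Arm 3's contribution only. None of this repairs the after-100 sample.

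**Counting through the next sample can overcount.** A first positive at ED 56 to 72 in a PUP may have arisen after ED 50. This is fair, and it is why the rates need an explicit label and the ED at first positive.

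**Confirmation and conditional harm.** SAP 4.7.1 requires confirmation at a subsequent visit, so an after-100 positive at End of Study counts only if the repeat test required by Protocol 8.6 is accepted. Harm needs a PTP first positive above ED 100, and none is documented. Both limit how often the problem bites; neither makes the rule right.

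**Conclusion.** The concern holds, and the rule must be fixed. As written, the three PTP rates do not measure incidence at the samples scheduled for them, and an inhibitor first found at the after-100-ED sample almost always enters none. At the assumed regular prophylaxis frequencies the after-100 sample misses its cap in every schedule starting at ED 0, and in 96 to 98 of 100 Arm 1 starting points. One such case in 200 turns 0.5% (0.01% to 2.75%) into 0/200 (upper limit 1.83%), so the primary PTP result can differ between protocol and SAP.

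The PUP effect is smaller. It concerns prophylaxis only, and Protocol 1.1 puts median onset at 12 EDs, so few cases would be lost; each moves a rate based on 24 subjects by 4.2 points. The conclusion rests on the literal ≤X wording and the visible text. It does not depend on a case having occurred, though actual harm does.

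**What to change.** 1. State in SAP 4.7.1 that the primary PTP and PUP incidences use the numerator and denominator of Protocol 11.3.3.2 (high-titer only for PUPs), with no ED cap. This also covers Arm 1 subjects who enter with 100 or more EDs, whom step 2 alone may miss.
2. For the secondary milestone rates in SAP 4.7.1 and Protocol 11.3.3.4.1, count confirmed central-laboratory inhibitors through the first sample at or after X EDs. Use as denominator the subjects with a valid sample at or after X EDs plus those with an earlier confirmed inhibitor. Replace the exclusion of subjects not tested at ≤X EDs to match, record the change in SAP 4.11, and label each rate as the first assessment after X EDs.
3. Report the actual ED at first positive for every case.

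**Cost.** No new data; wording changes in the SAP and in Protocol 11.3.3.4.1. The SAP change list records the PTP report as completed in November 2019, so the PTP inhibitor tables need a documented check, and a re-run if any case or denominator changes. The downside is that the 10-ED rate will include inhibitors found as late as about ED 24 to 42 (22 to 46 with the visit window), so it must carry its label and be read with the ED at first positive.

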##### The Inhibitor incidence after 50 Total EDs

- Numerators = Number of PTP subjects who develop inhibitors up to 50 EDs ( $\leq 50$  EDs)
- Denominators = Total number of PTPs with at least 50 EDs ( $\geq 50$  EDs) + subjects with less than 50 EDs with inhibitors. Subjects not tested at  $\leq 50$  EDs will be excluded.

##### The Inhibitor incidence after 100 Total EDs

- Numerators = Number of PTP subjects who develop inhibitors up to 100 EDs ( $\leq 100$  EDs)
- Denominators = Total number of PTPs with at least 100 EDs ( $\geq 100$  EDs) + subjects with less than 100 EDs with inhibitors. Subjects not tested at  $\leq 100$  EDs will be excluded.

CCI

Same algorithm will be applied for PUPs.

For PUPs incidence of transient inhibitors (negative results within 6 months after positive result) will be also provided.

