3.3 Planned Study Duration

The duration of the study for an individual subject is expected to be approximately 6 years to achieve the following number of EDs with rVIII-SingleChain:

- PTPs in Arm 1 may enroll immediately after participation in previous rVIII-SingleChain studies and continue treatment until achieving at least 100 EDs (including EDs from any previous rVIII-SingleChain study).

- Inhibitor-negative PUPs in Arm 2 will receive treatment in this study until they achieve 75 EDs with rVIII-SingleChain; the overall study duration is expected to be up to 6 years. Additional time of up to 3 years in the study may occur for PUPs that develop an inhibitor:
 - CCI [REDACTED]
 - For inhibitor-positive PUPs who remain in the **main study** who have achieved eradication, the End of Study Visit will occur when they complete the 12-month post eradication follow-up period in the main study. The maximum duration of the inhibitor treatment period is 24 months starting when the dose is initially adjusted to treat the inhibitor, and if no dose adjustment is performed to treat the inhibitor then the duration of inhibitor treatment will be from the date of inhibitor diagnosis.
- PTPs in Arm 3 will receive treatment in this study until they achieve at least 100 EDs with rVIII-SingleChain (excluding EDs from any previous rVIII-SingleChain study that the subject may have participated in).

In all study arms, subjects will complete the study as outlined in [Section 3.1](#) or until the study is terminated by the sponsor.

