8.10.6 End of Study

For subjects in all study arms, the End of Study Visit should take place at the end of the planned treatment period, ie:

- After at least 100 EDs in Arms 1 and 3 [PTPs].
- After 75 EDs if inhibitor negative.
- If inhibitor positive, after the 12-month post eradication follow up period or after 24 months of inhibitor treatment without CCI ().
- If the subject discontinues prematurely.
- If the sponsor terminates the study.

No further study-related procedures will be performed after the End of Study Visit, except for follow-up of ongoing AEs (see [Section 9.9](#)) and inhibitor SAEs in Arm 2 PUPs (see [Section 9.10](#)).

8.10.6.1 End of Study Visit for Arm 1

In **Arm 1**, the following procedures will be performed at the End of Study Visit:

- Obtain hemophilia A social history and activity level.
- Obtain blood sample for inhibitors to FVIII.
- Obtain virology retention sample.
- Review and collect of subject eDiary.
- Record investigator assessment for treatment efficacy of any treated bleeding episodes.
- Collect all vials (used, partially used, and unused) of rVIII-SingleChain.
- Assess drug accountability.
- Review AEs.
- Review concomitant medications.

8.10.6.2 End of Study Visit for Arms 2 and 3

In **Arms 2 and 3**, the following procedures will be performed at the End of Study Visit:

- Obtain hemophilia A social history and activity level.
- Obtain blood sample for serum chemistry and hematology.
- Vital signs.
- Physical examination.
- Record weight and height.
- Obtain blood sample for inhibitors to FVIII.
- Obtain blood sample for antibodies against rVIII-SingleChain and CHO proteins.
- Obtain virology retention sample.
- Review and collect of subject eDiary.
- Record investigator assessment for treatment efficacy of any treated bleeding episodes.
- Collect all vials (used, partially used, and unused) of rVIII-SingleChain.
- Perform drug accountability.
- Review AEs.
- Review concomitant medications.

9 Adverse Events

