## 3 Study Design

### 3.1 Discussion of Study Design

This multicenter, non-randomized, open-label, multiple-arm phase 3 extension study will continue to investigate the safety and efficacy of rVIII-SingleChain in PTPs and PUPs with severe hemophilia A. This study will evaluate the prophylaxis and on-demand treatment of bleeding episodes in at least 200 PTPs who achieve at least 100 EDs as well as in at least 50 PUPs. In Arms 1 and 3 (PTPs), each PTP will stay in this study until they have achieved at least 100 EDs, which overall is expected to take up to 5 years. In Arm 2 (PUPs), each PUP will stay in this study until they have achieved at least 75EDs, which overall is expected to take up to 5 years. A surgical substudy (open to subjects from all study arms) will investigate the use of rVIII-SingleChain in surgery. CCI

[Valentino et al., 2015].

Eligible subjects will be enrolled in 3 Arms, as detailed in [Section 2](#).

This study is designed to collect data on the use of rVIII-SingleChain to assess long-term safety and efficacy beyond the outcome from pre-marketing authorization clinical studies as well as to assess inhibitor development and characterize efficacy and safety of rVIII-SingleChain in PUPs. Inhibitor development is of particular interest for the safety of rVIII-SingleChain.

The preceding lead-in clinical studies, i.e. CSL627\_1001 and CSL627\_3002, are referred to as pivotal studies.

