#### The transient inhibitor incidence

- Numerators = Number of PUPs subjects who develop inhibitors and have subsequent negative results within 6 months, i.e. 183 days
- Denominators = Total number of PUPs who develop inhibitors

A two-sided 95% exact CI for the incidence of inhibitor formation will be calculated. If zero inhibitors are observed, then a one-sided 97.5% upper confidence limit will be calculated. SAS' FREQ procedure will be applied to produce an exact CI, which uses the Clopper-Pearson CI as the default method, however, Wald CIs will also be presented. The analysis will be performed also by race.

For PUPs, the incidence (with CI) of inhibitor formation to FVIII will be estimated also by Total EDs ranges. According to the Total EDs they were exposed at time of first positive FVIII inhibitor test PUPs will be classified into 0-10 EDs, >10-25 EDs, >25-50 and >50 EDs. Assessments at EDs=0 are defined as those assessments done before date and time or on the same date and time of first dose. If time of assessment or time of first dose is missing then the inhibitor result taken at the same date of the first dose will be considered as at EDs=0. An assessment done on the same date and time of a dose will be considered to be exposed to the number of EDs the subject has been exposed before that date and time. If time is missing for the assessment or the dose, then the assessment done on the same date of dose will be considered to be exposed to the EDs the subject has been exposed before the date of that dose.

Summaries of inhibitors assay test and inhibitor titer while subjects are inhibitor positive will be provided.

The incidence of inhibitor formation to FVIII will be also summarized at the assessment of 10, 50 and 100 EDs in the current study as collected in the eCRF.

Analysis will be performed overall, by region and considering the Japanese subgroup only.

CCI

CCI

CCI

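### SAP 4.7.1 extends its inhibitor-incidence algorithm to PUPs without limiting the exposure-day time points; a 100-ED PUP row would have an outcome-dependent denominator and be biased upward

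*SAP*

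**What the plan says.** SAP 4.7.1 sets out three incidences in turn, after 10, 50 and 100 Total EDs, each worded for PTPs. The 100-ED version reads "Denominators = Total number of PTPs with at least 100 EDs", and adds subjects below 100 EDs who have an inhibitor. Subjects not tested by 100 EDs are excluded. A redacted block follows, and then the sentence "Same algorithm will be applied for PUPs". Further on, the section plans that the incidence "will be also summarized at the assessment of 10, 50 and 100 EDs in the current study as collected in the eCRF", without naming an arm. It also asks for analyses by race, by region and for the Japanese subgroup.

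Follow-up in Arm 2 depends on inhibitor status. Protocol 3.3 states "Inhibitor-negative PUPs in Arm 2 will receive treatment in this study until they achieve 75 EDs with rVIII-SingleChain", and Protocol 8.10.6 places the End of Study Visit "After 75 EDs if inhibitor negative". For the others, Protocol 3.3 says "Additional time of up to 3 years in the study may occur for PUPs that develop an inhibitor". SAP 3.1 words the exit differently: "each PUP will stay in this study until they have achieved at least 75EDs".

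Where PUP time points for inhibitor incidence are named, they are 10 and 50 EDs: Protocol 2.2.2.2, Protocol 11.3.3.4.1 and SAP 2.2.2.

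**The concern.** For PTPs the 100-ED rule is sound, because they are followed to at least 100 EDs whether or not an inhibitor appears. In Arm 2, whether a boy counts in a 100-ED denominator depends on his outcome. One with an inhibitor counts at whatever ED he reached. One without an inhibitor who finishes at the planned 75 EDs does not count. The clause excluding subjects not tested by 100 EDs brings none of them back.

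A programmer following 4.7.1 as written could therefore produce a PUP row, with subgroup versions, that overstates incidence on a question of particular interest in this study. The Clopper-Pearson interval planned in that section covers sampling error, not selection. The protocol also cites evidence that almost all inhibitors have developed by 75 EDs, so going on to 100 EDs would add few cases while removing event-free boys.

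**Working it through.** The documents give no 100-ED figure for PUPs and no sample size calculation, so there is no stated result to reproduce. The rule can be evaluated directly.

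**Inputs**
- N = 24 PUPs (Protocol 11.1; SAP 3.9, Sample Size Estimation).
- x = PUPs with an inhibitor by 100 EDs. For illustration x = 8, which is 8/24 = 33.3%, near the 35.4% within 50 EDs that Protocol 1.1 cites. It is not a design assumption.
- k = inhibitor-negative PUPs with at least 100 EDs. This is not in the documents and is varied from 0 to N − x = 16.

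**Formula.** The 100-ED rule gives x/(x + k), while the cohort proportion is x/N. The first exceeds the second whenever k < N − x, so against the cohort proportion the error can only be upward.

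| k of 16 negatives | Row | Exact 95% CI |
|---|---|---|
| 0 | 8/8 = 100% | 63.1–100 |
| 2 | 8/10 = 80.0% | 44.4–97.5 |
| 4 | 8/12 = 66.7% | 34.9–90.1 |
| 6 | 8/14 = 57.1% | 28.9–82.3 |
| 8 | 8/16 = 50.0% | 24.7–75.3 |
| 12 | 8/20 = 40.0% | 19.1–63.9 |
| 16 | 8/24 = 33.3% | 15.6–55.3 |

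In the rows with k = 0, 2 and 4 the exact interval excludes the cohort value of 33.3%.

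**How large might k be under the 75-ED stop?** On prophylaxis, visits after 25 EDs are every 3 months, and a month is 28 days, so the interval is 84 days. Assume that End of Study falls at the first scheduled visit with at least 75 EDs and that counts are spread evenly over the possible values. The most a boy can then have is 74 plus one interval's EDs.
- Twice weekly: 74 + 24 = 98, so none reaches 100.
- Three times weekly: 74 + 36 = 110. Values run from 75 to 110, and 11 of these 36 (31%) are at least 100. Of 16 negatives that is about 5, giving 8/13 = 61.5%.
- Every second day: 74 + 42 = 116. Values run from 75 to 116, and 17 of these 42 (40%) are at least 100. Of 16 negatives that is about 6, giving 57.1%.

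On these assumptions the row lies between about 57% and 100%, against 33% for the cohort.

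**Sensitivity to incidence.** With x = 5 (5/24 = 20.8%, 19 negatives), the row is 5/5 = 100% at k = 0, 5/11 = 45.5% at k = 6 (31% of 19) and 5/13 = 38.5% at k = 8 (40% of 19).

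**At 50 EDs.** Inhibitor-negative boys are planned to go past 50 EDs. If all 16 do, and all 8 inhibitors have appeared by then, the same rule gives 8/24 = 33.3%. The distortion therefore comes from the 100-ED time point.

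**The case against.** The strongest reply is that no 100-ED PUP analysis is intended. Protocol 11.3.3.4.1, which the SAP sentence appears to carry over, analyses PUPs by analogy with PTPs but names 10 and 50 EDs. A new PUP time point is not among the readable entries of SAP 4.11. The SAP's PUP exposure ranges end in a single class above 50 EDs, and the table shells are in a separate document. A redacted block stands directly before the key sentence, so its full context cannot be seen. The eCRF summary at 10, 50 and 100 EDs matches assessments that Protocol 8.6.1 and Table 8 schedule for Arms 1 and 3 only, while PUPs are tested at all scheduled visits. All of this stands. It makes the point an unrestricted instruction that conflicts with the named endpoints, not a declared 100-ED PUP endpoint.

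The size is also open. A reader might infer that the denominator would hold mainly boys with inhibitors and that the result would drift towards 100%. The documents do not establish that. Protocol 1.3 records a former target of 150 EDs for all PUPs, and at 2 to 3 injections a week 100 EDs takes about 100/3 = 33 to 100/2 = 50 weeks. Some inhibitor-negative boys may therefore have passed 100 EDs already. SAP 3.1 allows more than 75 EDs, and overshoot between visits is not rare on frequent regimens. With x = 8, inhibitor cases are the majority only if k is below 8; with x = 5 and k of 6 to 8 they are not.

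Finally, SAP 3.5.6 suppresses tables for subgroups of 3 or fewer, which could remove some of the race, region or Japan versions.

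None of this supplies the missing limit in 4.7.1 or changes the direction of the bias if the row is produced.

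**Conclusion.** Wrong as written. The visible text of SAP 4.7.1 applies to PUPs an algorithm that includes a 100-ED denominator. This conflicts with the 10- and 50-ED time points in Protocol 11.3.3.4.1 and SAP 2.2.2, and with the planned 75-ED exit of inhibitor-negative PUPs. Followed literally, it yields an incidence biased upward relative to the cohort proportion.

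In the illustration the row lies anywhere from 33% to 100%. The narrower 57% to 100% rests on the 75-ED stop, 84-day visit spacing, an even spread of ED counts and 8 inhibitors in 24 boys. It does not allow for boys who passed 100 EDs under the former target. No point estimate of the bias is possible without knowing k.

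A reader might also take this to undermine the main PUP safety result. It does not: Protocol 11.3.3.2 bases the primary PUP incidence, high-titer inhibitors, on a 50-ED denominator. The 10- and 50-ED secondary endpoints are likewise outside this problem.

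**What to change.** Add to SAP 4.7.1 that for PUPs the algorithm applies at 10 and 50 EDs only, as in Protocol 11.3.3.4.1, and that the 100-ED incidence and the 10/50/100-ED eCRF summary apply to Arms 1 and 3. Bring the table shells into line.

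For PUP exposure beyond 50 EDs, use the ED-based cumulative incidence curve recorded in the SAP's List of Substantial Changes, with each boy without an inhibitor censored at his last tested ED and the numbers at risk shown. Boys who stop at 75 EDs then contribute up to the point at which they were last observed.

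The cost is a sentence or two in the SAP and a check of the shells. No new data are needed, and neither the PTP analysis nor the primary PUP endpoint changes.
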